contact with any potential participants. Once a potential participant expresses verbal interest, additional study team members may continue the informed consent and eligibility screening process. The Site Investigator will perform the History and Physical (H&PE) and INSCSCI examinations. If there is skin breakdown or an abrasion due to contact friction with the exoskeleton, the Site Investigator/Physician works with the Trainers and participant to determine if the participant needs to take time off to allow it to heal or if the addition of padding or equipment adjustments is sufficient to prevent further breakdown and the participant may continue in the training sessions. Additional, co-Investigators who are physicians are welcome to help defray some of the workload from the Site Investigator; however, the Site Investigator will ultimately be responsible for overseeing all conduct related to the CS #2003 at their site. Co-Investigators from other disciplines are also welcome to be part of this study. Each site will need to provide a clear description of additional co-Investigator roles in the study.

The proposed study will require fifteen sites. Each site will have four full time staff who would be solely dedicated to the conduct of the study (1 ReWalk Trainer, 2 Assistant ReWalk Trainers and 1 Study Coordinator). Two staff persons are needed during the initial EAW Training phase for each of the participants. The ReWalk Trainer will have a clinically relevant professional background such as a biomedical, electrical or mechanical engineer, physical therapist, exercise physiologist, occupational therapist, nurse, athletic trainer, or equivalent. The ReWalk Trainer will be responsible for the screening of participants, scheduling, fitting and training of the exoskeleton, and mobility measurement aspects of the protocol. The ReWalk Trainer and Assistant ReWalk Trainers will be responsible for the administrative paperwork, assist with eligibility screening, assist with the informed consent process, scheduling of participants, the home evaluation when needed, the EAW training, weekly and monthly participant contact during the orientation and home use phases of the study, ensuring the Usual Activity log and EAW Activity Log are completed, reporting adverse events, and all other aspects of the study protocol. The Assistant ReWalk Trainers will assist the trainer in all EAW aspects of the study. All of the Trainers must be capable of assisting with the EAW training and as such, are expected to be healthy and free of back or other medical problems that would be contraindicated for lifting and carrying 60 pounds across a room. The Trainers must be able to lift the exoskeleton from one chair to another, or to place one in or take it out of the trunk of a car or van.

CS #2003 study will also support a Site Coordinator. The Site Coordinator will be responsible for the administration of the QOL outcome surveys, local Research & Development and CIRB application paperwork and assisting with scheduling and data entry. The study Coordinators may

be physical therapists, PT assistants, exercise physiologists, nurses, nurse assistants, research health science specialists or technicians, or other comparable disciplines that have experience with research methods and procedures and experience and knowledge about persons with SCI. Approved and classified PDs will be provided to the sites for recruitment of study personnel if requested.

Each Site will need the following:

1. Access to a bone mineral densitometer or space for the ones to be provided by CS #2003;

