
B. Randomization System

An Interactive Touch Tone Randomization System (ITTRS) will be used for randomization within

each site. This system will be accessed through the Cooperative Studies Program Coordinating Center at the Perry Point VA Medical Center, [name].

C. Population to be Studied

One hundred-sixty male or female Veteran or active duty military personnel with chronic SCI, of \geq six months duration, who are \geq 18 years of age, and who are medically stable and wheelchair users for indoor and outdoor mobility, will be eligible for screening to be enrolled in the study. All potential participants will be Veterans or active duty military personnel with SCI who are affiliated with or transferred to one of the fifteen VA SCI Services that will be participating in this study. Study participants will generally be outpatients with the exception of those inpatients who meet the eligibility criteria and are approved by the Site Investigator (e.g., some inpatients may have been admitted for a wheelchair fitting or another non-medical reason). Non-veterans, other than active duty military personnel getting treatment at the VA, will not be eligible to participate. Eighty participants will receive SOC plus EAW (Intervention group) and 80 will receive SOC (Control group). It is expected that no more than 15% of the participants will withdraw early (dropout rate) and this attrition rate is expected to be evenly distributed between the two groups (12 withdrawals/group). One hundred-thirty-six participants are expected to complete the study (68/group).

V. INTERVENTION AND METHODS OF TREATMENT

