Each participant will be required to have an EAW companion that will accompany them when the participant is using the device. There may be multiple people trained to be the EAW companion. An EAW companion will always need to be in close proximity to the participant when the system is in use while in the home or community environments. The companion's job is to be there to assist the participant with tasks such as navigating doors, bring them a chair, picking up items needed from the floor, countertops, furniture, tabletops, etc., provide close guard or contact assist when necessary, moving the device for donning or after donning, and to assist the participant with device checking, battery charging and storage. If a participant does not have a suitable companion, then they will not be eligible to participate in the study and are considered to be a screening failure.

Training of more than one companion is strongly encouraged. The potential participant may have up to three companions who share in the EAW training with the participant. All companions will be provided a separate consenting process and will either sign an informed consent form and HIPAA authorization or assent over the phone to be enrolled. If a companion withdraws during the Intervention Phase and no other companion was trained or available, the participant must complete additional companion(s) training. The new companion must pass the EAW Advanced Skills Test with the participant to be given clearance to return to the home/community use environment with the exoskeleton.

The companion screening criteria are meant to be general guidelines, but it is ultimately in the clinical judgment of the Site Physician to permit an acceptable companion.

Companion Criteria:

1. Male or female, age ≥ 18 years;
2. Demonstrates understanding of the time commitment to be a companion (to be available for approximately one-third of the training sessions, and walking at home or in the community with the participant);
3. The companion and the user are willing to receive training on how to assist the user with donning/doffing the device, use of the controller, and performing the standing, sitting, walking, and stopping skills while in the device;
4. The companion and the user are able to understand how to operate, charge, and maintain the device;

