During the weekly contact with the participant, the study staff will inquire about the frequency of walking and the availability of the companion. If the companion has not been able to walk with the participant in a past week, the study staff will try to resolve the problems. Additional companions will be suggested. Availability of the EAW companion(s) is an important consideration and a close eye on this process will be necessary. Since these exoskeletal devices are going to require walking companions as per the FDA, it will be important to know the feasibility of our Veterans and military members with SCI to have viable walking companions for use of an exoskeleton in the home/community environment. The number of eligible companions and the actual amount of walking time that the companions are available for the participants during the home-use phase can be determined in the Feasibility component of the study. If the companion requirement proves to be an obstacle during the feasibility, it can be addressed with each case and solutions can be made available for all study participants. If a companion is lost or withdraws from the study, then the participant will be obligated to re-train another companion, or the participant will be terminated from the study, an outcome that will be strenuously avoided. Of note, as a consequence of this clinical trial, it will also be determined if identifying a companion is a major obstacle to the use of the exoskeleton in our Veteran or military member population with SCI because, as previously stated, these devices cannot be prescribed for home use without a companion in attendance when this device is being used.

H. EAW Advanced Skills Test

The EAW Advanced Skills are in addition to the EAW Basic Skills. The EAW Advanced Skills Test will be passed by the participant and their companion(s) prior to being sent home with an

exoskeleton and as soon during the training course as the ReWalk Trainers and the participants (with their companions) feel they can achieve the skills (at a minimum of 20 sessions). However, if by 30 sessions the participants are unable to achieve these skills, they will not be sent home with the device and will be treated as a study “failure”. Participants (with their companions) will need to demonstrate the following skills according to the SOP manual:

- Transfer into and out of the exoskeleton;

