2. PROMIS Sleep Disturbance T score;
3. Assessment of bowel function for:
 - a. Bowel evacuation (BE) time per episode in the past week,
 - b. Frequency of BE episodes,
 - c. Number of self-reported “natural” bowel movements in the past week,
 - d. Frequency of digit stimulation in the past week,
 - e. Stool consistency by the Bristol Stool Scale in the past week, and
 - f. Frequency of enema use and amount of laxatives and/or stool softener used in the past month, and
 - g. Frequency of bowel incontinence/accidents in the past month;
4. SCI-QOL Physical-Medical Health for bladder complications (scale) and pain behavior (scale);
5. SCI-QOL Emotional Health for positive affect and well-being, depression, anxiety, stigma, resilience, grief-loss, self-evaluation, and trauma;
6. SCI-QOL Social Participation for ability to participate in social roles and activities, satisfaction with social roles and activities, and independence;
7. SCI Functional Index (SCI-FI) for Physical Function for basic mobility, ambulation, fine motor, self-care, wheelchair mobility, and assistive technologies;
8. Abdominal fat mass by DXA scan (this is acquired as part of the total body scan);

9. Lipid profile analysis for HDL-c, LDL-C, TG, and TC will be shipped to the Chair's Office for batch analysis by the JJPVAMC laboratory (results will be blinded); and
10. FPG and FPI for HOMA-IR calculation. FPG and FPI will be shipped to the Chair's Office for batch analysis by their Core research laboratory.

D. Additional Assessments

1. EAW Basic Skills Test will be performed:
 - a. During the five-session basic EAW Training (both groups),
 - b. Post Training phase (Intervention group only), and
 - c. Post 4-month Intervention phase (Intervention group only);
2. EAW Advanced Skills Test performed:
 - a. Post Training phase (Intervention group only) and
 - b. Post 4-month Intervention Phase (Intervention group only).

E. Quality Control (non-outcome) Measurements

1. Weekly SOC activities (Usual Activity Log) will be recorded for wheelchair activities and other, non-wheelchair activities (e.g., standing frame, swimming, or other non-wheelchair activities). This is measured weekly in both groups.
2. In the Intervention group only;
 - a. Weekly EAW Activity Log in the Intervention group only,
 - b. Weekly number of steps taken recorded on the step counter, and

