As part of the orientation and training for each participant on the device, the expected occurrence of routine AEs will be described to the participants, including that they may experience skin abrasions, and hand, shoulder or any other joint discomfort. During the five-session Basic Training and in the Screening Phase and the Orientation/Training Phase, participants will be asked during each session if they are experiencing any discomfort or pain. Hand or shoulder discomfort, if they occur, are expected to occur early on in training when the participant is learning to use the device. Participants who report any pain or other medical problem will be referred to the Site physician. The Site physician will be responsible for taking the appropriate course of action for the AE or SAE. The study staff will be responsible for recording the occurrence of AEs or SAEs appropriately, as they occur. Additionally, the SMART unit will be charged with monitoring the informed consent documentations, source documents, AE and SAE forms, as well as assessing if the Site study team is carrying out the study correctly.

The Site Investigator will be responsible for monitoring these events on a regular basis at his/her site. The immediate and ongoing safety review of study data to monitor for evidence of adverse events will be conducted by the Cooperative Studies Program Clinical Research Pharmacy Coordinating Center (CSPCRPCC) in Albuquerque, NM. The Data Monitoring Committee (DMC) will review AEs and SAEs on a regular basis.

H. Participant Safety Stopping Rules

The Site Physician will make the decision for participants who have a safety or medical concern such as: skin breakdown, edema, joint discomfort, muscle soreness, extreme fatigue, or any other medical condition as to whether they are to be continued as is, continued with modifications to the equipment, temporarily discontinued, or withdrawn from the study. Re-entry to the Training or Intervention phases of the study will be based on the Site Physician's medical clearance and the participant's safety to begin again.

I. Site Participation Stopping Rules

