The primary analysis will be based on an intent-to-treat (ITT) model. All participants who are randomized will be included for both groups, whether they are study completers (participants who complete the study through the four-month intervention phase) or early terminators (drop-outs). In order to test the hypotheses for the primary and major secondary outcome measures, each randomized participant will be deemed a success or failure at attaining: 1) ≥ 4.0 point improvement in the MCS of the VR-36, 2) $\geq 10\%$ improvement in the SCI-QOL bladder management difficulties, bowel management difficulties and pain interference sum T score, and

3) ≥ 1 kg. total body fat mass loss. For each of the outcomes, the proportion of participants successful at achieving a clinically significant improvement will be compared between the two groups (Intervention vs. Control) using a chi-square analysis. These will constitute the primary and major secondary efficacy analyses. Participants who drop out will be treated as failures. As such, by design, there will be no missing data: participants either meet the outcome criteria (successes), do not meet these criteria (failures) or they drop out (also failures).

G. Secondary Analyses

In addition to the primary analysis, several secondary analyses will be performed and are described below.

1. Analyses will be performed that include only those participants who complete the study (excluding drop-outs):
 - a) Chi-square analyses of the primary and major secondary outcome measures (proportion of successes) will be repeated for only those participants who complete the 4-month intervention phase.
 - b) Analyses of the MCS/VR-36, SCI-QOL, total body fat mass loss, Global Impression of Change and other secondary outcome measures will include comparisons of the mean difference scores (change from baseline to the end of the intervention phase) of these outcome variables using t-tests.

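### Unreplaced companion loss ends study participation rather than device use alone, so obtainable month-4 outcomes become automatic failures, in practice mainly in the Intervention arm

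*Combined protocol and SAP*

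**What the plan says.** Section VIII.G (EAW Companion Training) deals with companion loss twice. Its earlier paragraph says: "If a companion withdraws during the Intervention Phase and no other companion was trained or available, the participant must complete additional companion(s) training". It adds: "The new companion must pass the EAW Advanced Skills Test with the participant to be given clearance to return" to home or community use, and it does not mention leaving the study. The closing paragraph says that "the participant will be obligated to re-train another companion, or the participant will be terminated from the study", and calls termination "an outcome that will be strenuously avoided". Neither paragraph names an arm.

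Section XIII.F equates early terminators with drop-outs and states: "Participants who drop out will be treated as failures". This applies to MCS/VR-36, to the SCI-QOL sum score and to total body fat mass. No section provides for a month-4 assessment of a participant who has been terminated.

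Section IV.C allows for 15% withdrawal, 12 per group, and says that "this attrition rate is expected to be evenly distributed between the two groups".

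**The concern.** The companion requirement governs use of the exoskeleton, but the stated consequence of not meeting it is removal from the trial. The main outcomes do not depend on the companion. Under IX.F, VR-36 and SCI-QOL are interviews that may be done by phone. Fat mass is a DXA scan.

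A participant who loses a companion in month 3 and cannot find another could still be assessed at month 4, and might meet a success criterion. Under the rule as written that participant is a failure on all three main outcomes, whatever the measurements would have shown. If this happens mostly in one arm, the primary comparison sets measured response plus companion retention in the Intervention arm against measured response alone in the Control arm. The effect is a lower Intervention success rate and lower power. Companion availability is a named feasibility question in VIII.G and XIII.C, so the event is foreseen.

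**Working it through.** **Which arm the rule reaches.**
- All participants need a companion at screening.
- After randomization, home use of the device belongs to the Intervention arm (III.B).
- The Advanced Skills Test that a replacement companion must pass is listed in IX.D as "Post Training phase (Intervention group only").
- Controls have no device during the outcome period. Their companions have one further role, the companion-rated Global Impression of Change, which is a secondary outcome.
- That the rule acts mainly in the Intervention arm is therefore an inference from these sections, not something the plan states.

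**Reproducing Table 7.** The inputs are two-sided alpha 0.025 (z = 2.2414), control proportion 0.10, and Intervention proportions 0.333, 0.42 and 0.35 with power 80%, 95% and 85%. With d = p2 − p1 and p̄ = (p1 + p2)/2:

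- n0 = [z√(2p̄(1−p̄)) + z_power√(p1(1−p1) + p2(1−p2))]² / d²
- continuity-corrected n = (n0/4)[1 + √(1 + 4/(n0·d))]²

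| Outcome | n0 | Corrected n | n/0.85 | Table 7 |
|---|---|---|---|---|
| MCS | 58.1 | 66.4 → 67 | 78.8 → 79 | 67, 79 |
| SCI-QOL | 53.5 | 59.6 → 60 | 70.6 → 71 | 60, 71 |
| Fat mass | 58.2 | 66.0 → 66 | 77.6 → 78 | 66, 78 |

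The method matches the plan.

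**Effect of the rule.** Let c be the share of the Intervention arm terminated for unreplaced companion loss, on top of 15% attrition in each arm scored as failure. The documents give no value for c, so 5%, 10% and 15% (4, 8 and 12 of 80) are assumptions. Success is then 0.10 × 0.85 = 0.085 in Control and p2 × (0.85 − c) in Intervention. Power at 80 per group comes from inverting the two formulas above. For MCS:

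| c | Intervention success | z_power | Power |
|---|---|---|---|
| 0 | 0.333 × 0.85 = 0.283 | 0.814 | 79% |
| 5% | 0.333 × 0.80 = 0.266 | 0.582 | 72% |
| 10% | 0.333 × 0.75 = 0.250 | 0.347 | 64% |
| 15% | 0.333 × 0.70 = 0.233 | 0.106 | 54% |

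On the same basis, SCI-QOL power goes from 97% to 94%, 89% and 83%, and fat mass power from 84% to 78%, 70% and 61%.

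**What follow-up would recover.** Take MCS at c = 10%, with those participants assessed and scored as observed.
- If they respond at the 10% control rate, Intervention success is 0.250 + 0.10 × 0.10 = 0.260 and power is 69%.
- If they respond at the planned 33.3%, it is 0.250 + 0.10 × 0.333 = 0.283 and power is 79%.

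**The case against.** The strongest reply is that termination is a last resort and that failure is a defensible score for it.

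- **Safeguards.** Re-training comes first, up to three companions are allowed, training more than one is encouraged, and availability is checked weekly. A reader might infer that losing a companion removes the participant automatically; the text does not support that. Only unreplaced loss does so. These points limit how often the rule applies but do not change its effect when it does.
- **The two VIII.G paragraphs.** A reader might call them contradictory. They share the same first step; one adds a fallback on which the other is silent. They need aligning, but they do not prescribe opposite actions.
- **A composite endpoint.** The device cannot be used at home without a companion, so failure could be a deliberate, conservative score. The plan does label failing the Advanced Skills Test a study failure (III.A, VIII.H). It does not label companion loss that way, and XIII.F defines success by measured change.
- **Other analyses.** XIII.G plans repeated-measures models on all available data, with multiple imputation if missing at random is not tenable, so earlier values from terminated participants are kept there. This is a real mitigation for the secondary analyses. It does not reach the primary chi-square test, and the completer analyses still lose these participants.
- **Fat loss in training.** II.D expects at least 50% of the Intervention group to lose 1.0 kg by the end of training. A reader might take that as the share of successes thrown away. The same section expects 35% at the endpoint, so the 50% cannot be used for month 4.
- **Section XI.H.** Its options include "temporarily discontinued, or withdrawn from the study", and a reader might see the same fault there. That section is a Site Physician's safety decision covering any medical condition and naming no arm. It does not support the point.

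**Conclusion.** The point stands in a limited form. As written, unreplaced companion loss ends study participation and becomes a failure on all three main outcomes, although the month-4 data could be obtained. The one-sided effect is a sound inference from where the device is used, and it does not fit the even-attrition assumption.

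The bias runs against the device. It could hide a benefit; a reader should not infer a false positive in the device's favour.

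The size cannot be fixed from the documents. The MCS figures of 72%, 64% and 54% assume that companion losses are additional to the 15% attrition and that those participants would otherwise have responded at the planned rate. If companion loss already falls within the planned 15%, the loss is smaller. If participants without the device respond only at the control rate, follow-up at c = 10% recovers about 5 points of power (64% to 69%) rather than the full 15 (64% to 79%). MCS has the least margin and is the most exposed; SCI-QOL is the most robust. The plan should be changed because the correction is cheap and the event is foreseen, not because a large loss has been shown.

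**What to change.** Reconcile the two VIII.G paragraphs so that unreplaced companion loss is recorded as the end or suspension of home/community device use, not as termination from the study. Weekly contact and the scheduled month-2 and month-4 outcome assessments continue where the participant agrees.

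In XIII.F, state that participants who stop device use for this reason but are assessed at month 4 are scored on their observed values. Keep drop-out as failure for those who are not assessed.

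Leave the companion requirement for device use and the Site Physician's discretion in XI.H as they are.

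The cost is a short amendment, since these assessments are already scheduled for every randomized participant. The downside is that a few people who have stopped using the device are asked to attend the remaining visits.
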